10.3.5 Reporting of SAEs

SAE Reporting to the Pharmacovigilance CRO via an Electronic Data Collection Tool

- The primary mechanism for reporting an SAE to the pharmacovigilance CRO will be the electronic data collection tool.
- If the electronic system is unavailable, then the site will use the paper SAE data collection tool to report the event within 24 hours.
- The site will enter the SAE data into the electronic system as soon as it becomes available.
- After the study is completed at a given site, the electronic data collection tool will be taken off-line to prevent the entry of new data or changes to existing data.
- If a site receives a report of a new SAE from a study participant or receives updated data on a previously reported SAE after the electronic data collection tool has been taken off-line, then the site can report this information on a paper SAE form or to the pharmacovigilance CRO by telephone.

10.4 Appendix 4: Abbreviations

Abbreviation	Definition for Term
21 CFR	Code of Federal Regulations Title 21
ADA	anti-drug antibody
AE	adverse event
ALT	alanine aminotransferase
APGAR	Appearance, Pulse, Grimace, Activity, and Respiration
AST	aspartate aminotransferase
AUC	area under the (RLYB212) concentration versus time curve
AUC _{0-inf}	area under the concentration-time curve from time zero extrapolated to infinity
cffDNA	cell-free fetal DNA
CIOMS	Council for International Organizations of Medical Sciences
CL	clearance
CL/F	apparent clearance
C _{max}	maximum serum concentration
CONSORT	Consolidated Standards of Reporting Trials
CRF	case report form
CRO	Contract Research Organization
CRP	C-reactive protein
CTCAE	common terminology criteria for adverse events
DMC	Data Monitoring Committee
ECG	electrocardiogram
EOS	end of study
FNAIT	fetal and neonatal alloimmune thrombocytopenia
GCP	Good Clinical Practice
GGT	gamma glutamyl transferase
GLP	Good Laboratory Practice
GW	Gestational Week
HBV	hepatitis B virus
HCV	hepatitis C virus
HDFN	hemolytic disease of the fetus and newborn
HIPAA	Health Insurance Portability and Accountability Act
HLA	human leukocyte antigen
HPA	human platelet antigen
HPLC	high performance liquid chromatography
ICF	informed consent form

Abbreviation	Definition for Term
ICH	intracranial hemorrhage
ICTMG	International Collaboration for Transfusion Medicine Guidelines
IEC	Independent Ethics Committee
Ig	immunoglobulin
IRB	Institutional Review Board
ISUOG	International Society of Ultrasound in Obstetrics & Gynecology
ITP	immune thrombocytopenia
IVIG	intravenous immunoglobulin
k_a	absorption rate constant
LDH	lactate dehydrogenase
LLOQ	lower limit of quantification
mAb	monoclonal antibody
MCH	mean corpuscular hemoglobin
MCHC	mean corpuscular hemoglobin concentration
MCV	mean corpuscular volume
MedDRA	Medical Dictionary for Regulatory Activities
PD	pharmacodynamic(s)
PK	pharmacokinetic(s)
PoM/PoC	proof of mechanism/proof of concept
PT	preferred term
Q4W	every 4 weeks
RBC	red blood cell
RhD	Rhesus D
SAE	serious adverse event
SAP	statistical analysis plan
SC	subcutaneous(ly)
SGOT	serum glutamic oxaloacetic transaminase
SGPT	serum glutamic pyruvic transaminase
SoA	schedule of activities
SOC	system organ class
SUSAR	suspected unexpected serious adverse reaction
$t_{1/2}$	half-life
TCR	tissue cross reactivity
TEAE	treatment-emergent adverse event

Abbreviation	Definition for Term
TK	toxicokinetic(s)
t _{max}	time to maximum (RLYB212) concentration
ULN	upper limit of normal
Vd	volume of distribution
WBC	white blood cell
WT	wild-type

10.5 Appendix 5: Protocol Amendment History

Version 4.0 (14 October 2024) superseding Version 3.0 (25 September 2024)

Rationale:

The SoA was updated to indicate that samples for hematology, chemistry, coagulation, and CRP assessments will be collected at Screening Part 2, Visit 2.

Version 3.0 (25 September 2024) superseding Version 2.0 (04 September 2024)

Rationale:

The following changes were made based on feedback received from the European Medicines Agency (EMA):

- Follow-up of the infant to 12 months of age; modifications were incorporated in the Synopsis, Schema/SoA, Objectives/Endpoints, End of Study Definition and Study Assessments and Procedures.

In addition, corrected EU CT number (removal of submission number).

Version 2.0 (04 September 2024) superseding Version 1.1 (23 August 2024).

Rationale:

The following changes were made based on feedback received from the European Medicines Agency (EMA):

- Included clarification that the occurrence of neonatal thrombocytopenia following antenatal RLYB212 administration will be evaluated based on the umbilical cord sample taken at parturition.
- Updated Exclusion Criteria at Screening Part 2:
 - Revised exclusion criterion 4 to: “Any participant with a history of past or current intravenous immunoglobulin (IVIG) use for an underlying disease (eg, autoimmune disease)”
 - Replaced exclusion criterion 7 with new criterion: “Participants with an in vitro fertilized pregnancy or serving as pregnancy surrogates”
- Clarified that broad spectrum immunosuppressant agents and IVIG are not allowed as concomitant medications with RLYB212 administration. If such treatments are required, RLYB212 will be discontinued but the participant will continue to be followed in the study.

- Replaced statement that vaccinations are not allowed within 30 days of screening until 30 days after the last dose of study drug, with “Routine vaccines, given at recommended times during or immediately after pregnancy, will be allowed in the study.”
- Clarified that up to 4 participants may be replaced if *assigned to study drug* but did not receive the study drug.
- Removed statements that samples collected as part of the screening and monitoring procedures may be retained for the purposes of analytical method validation, or for optional exploratory research.

In addition:

- The description of the sub-study was changed to “non-interventional (observational)”.
- For clarity, reference to “live birth” was revised to “full term birth”, where applicable.
- Updated the window for the last dose of RLYB212 to be administered from “within 72 hours of parturition” to “within 24 hours (± 24 hours) of parturition”.
- Included additional explanatory notes to the SoAs; removed “drug testing” from the SoA (Table 1-3); and removed “neonatal platelet count” from the SoA (Table 1-3), as it is addressed by the “cord blood sample” assessment.
- Paragraph on Lifestyle Considerations was simplified.
- Removed references to a Study Reference Manual (not applicable to the study).
- Removed appendix on liver safety (as this was addressed in Phase 1 studies).

Version 1.1 (23 August 2024) superseding Version 1.0 (11 March 2024).

Rationale:

The following changes were made based on feedback received from the United Kingdom Medicines and Healthcare product Regulatory Agency (MHRA), in addition to including the NCT number on the title page:

- Included a description in the protocol of the composition of the independent data monitoring committee that will be overseeing the safety of study participants.
- Included the requirement that after an initial AE/SAE report, the investigator must proactively follow each participant or fetus/neonate/infant at subsequent visits/contacts. All SAEs for the participant or fetus/neonate/infant will be followed until resolution, stabilization, the event is otherwise explained, or the participant is lost to follow-up.

2.0 (Amendment)	26AUG2025	Added section 4.9 “Changes in the Conduct of the Study or Planned Analyses” describing early termination and use of participant level listings only. Statistical analyses and TLFs described in the original SAP will not be performed. Corrected typos and updated lab table 5 based on protocol version 4.0.	Early termination of the study due to Phase 2 PK data indicating that the RLYB212 dose regimen could not achieve predicted target concentration or the minimum concentration required for efficacy; only one participant enrolled. Strategic reduction in scope of TLFs for final analysis.

Project Document Version No.:2.0; Document Effective Date: Date of last signature

TP-GDO-WW-016-09

Effective Date: 22 Dec 21

Related to: SOP-GDO-WW-019

Page 6 of 70

1. Introduction

RLYB212 is a recombinant human monoclonal anti-human platelet antigen (HPA)-1a immunoglobulin G (IgG)1κ antibody designed to selectively bind to HPA-1a positive fetal-derived cells or cell fragments present in the maternal circulation. The therapeutic goal of RLYB212 is to drive rapid and complete elimination of HPA-1a positive fetal antigen from the maternal circulation in HPA-1b/b pregnant women and prevent maternal HPA-1a alloimmunization (see protocol section 2.1).

This is a Phase 2, multicenter, open-label study to evaluate the pharmacokinetics and safety of RLYB212 in HPA-1b/b pregnant women at higher risk for HPA-1a alloimmunization and FNAIT.

A non-interventional (observational) sub-study (IPA2202A) is planned based on the phased approach to participant enrollment that results from the sequential cohort design. Because of the rarity of the potential occurrence of HPA-1a alloimmunization, the non-interventional (observational) sub-study will serve to augment an ongoing FNAIT Natural History Study (NCT05345561), ie, generating natural history data on the occurrence of HPA-1a alloimmunization and pregnancy/neonatal outcomes in women at higher risk for HPA-1a alloimmunization.

The analyses described in this SAP are based upon the following study documents:

- Clinical Study Protocol v 4.0 October 14, 2024 English IPA2202.
- 284014 Unique CRF v 1.0 27 Sep 2024.

1.1. Objectives, and Endpoints

1.1.1. Objectives and Endpoints (Interventional/Study IPA2202)

Objectives	Endpoints
Primary	
To evaluate the PK profile of RLYB212 during pregnancy following repeat SC administration	
Maternal PK parameters, e.g.,
 
• half-life of RLYB212 ($t_{1/2}$)• maximum RLYB212 concentration (C_{max})• time to maximum RLYB212 concentration (t_{max})• apparent clearance (CL/F) of RLYB212• apparent volume of distribution (Vd)• area under the RLYB212 concentration versus time curve (AUC)
To assess maternal and fetal safety of RLYB212 during pregnancy	
• Type, seriousness, and incidence of AEs• Physical examination findings• Vital signs• Maternal clinical laboratory values• ECG• Obstetric/fetal doppler ultrasound

Parexel International

Rallybio IPA, LLC
IPA2202

Statistical Analysis Plan

Secondary	
To evaluate RLYB212 exposure in the neonate at delivery	
 Concentration of RLYB212 in cord blood
To assess the safety of RLYB212 in the HPA-1a positive neonate	
 Type, seriousness, and incidence of AEs, including fetal/neonatal AEs Physical examination findings, including APGAR score Vital signs
To assess the immunogenicity of RLYB212	
 Development of ADAs
To assess pregnancy and neonatal outcomes following antenatal RLYB212 administration	
 Number of spontaneous abortions Number of elective abortions Number of stillbirths Number of premature births Number of full-term births (≥ 37 completed weeks of gestation) Overall health and development of infants at 4-6 weeks and 12 months of age
To assess the occurrence of neonatal thrombocytopenia following antenatal RLYB212 administration	
 Neonatal thrombocytopenia^a and severe neonatal thrombocytopenia
To assess the occurrence of HPA-1a alloimmunization	
 Presence of maternal anti-HPA-1a alloantibodies at Week 10 post pregnancy^b

^aEvaluation of neonatal thrombocytopenia will be based on the umbilical cord sample taken at parturition.

^bFor pregnancies that do not result in a live birth, the assessment of alloimmunization will be at 10 weeks from the date of the pregnancy-terminating event (ie, abortion [spontaneous/elective] or stillbirth).

RLYB212 drug concentrations will be summarized and listed in CSR. Maternal PK parameters, not part of the CSR will be explained outside of this SAP.

Project Document Version No.:2.0; Document Effective Date: Date of last signature

TP-GDO-WW-016-09

Effective Date: 22 Dec 21

Related to: SOP-GDO-WW-019

Page 9 of 70

1.1.2. Objectives and Endpoints (Non-interventional [Observational])/Study IPA2202A

Objective	Endpoint

 To inform the frequency of HPA-1a alloimmunization among pregnant women identified at higher FNAIT risk. 	
 Occurrence of anti-HPA-1a maternal alloimmunization at Week 10 postpartum^a

 To inform the frequency of pregnancy outcomes among pregnant women identified at higher FNAIT risk. 	
 Rate of spontaneous abortion, defined as non-deliberate fetal death which occurs prior to 19 weeks of gestation. Rate of elective abortion, defined as deliberate termination of pregnancy at any time in gestation Rate of stillbirth, defined as non-deliberate fetal death anytime in gestation on or after 19 weeks of gestation Rate of premature birth, defined as live birth prior to 37 completed weeks of gestation Rate of full-term birth (≥ 37 completed weeks of gestation)

 To inform the frequency, where data are available, of neonatal thrombocytopenia in infants born to women who have alloimmunized, as determined by detectable anti-HPA-1a antibody at Week 10 postpartum^a. 	
 Neonatal thrombocytopenia and severe neonatal thrombocytopenia, as determined by a platelet count $< 150 \times 10^9/L$ and $< 50 \times 10^9/L$, respectively, where data are available

^aFor pregnancies that do not result in a live birth, the assessment of alloimmunization will be at 10 weeks from the date of the pregnancy-terminating event (ie, abortion [spontaneous/elective] or stillbirth).

The purpose of the IPA2202 study is to follow the PK and Safety of 8 participants that receive RLYB212. The participants that are identified at higher risk for FNAIT that do not enter the interventional study will be asked to consent for the non-interventional (observational) sub-study (IPA2202A). These observational participants will be followed per protocol through parturition and assessed 10 weeks postpartum (or end of the pregnancy) for the occurrence of

alloimmunization. The data from these observational participants will be merged with the IPA2002 study dataset and analyzed as one. Only IPA2202A participants' disposition will be summarized along with IPA2202 study summary. Hence objectives and endpoints of IPA2202A participants will not be discussed in this document.

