3. Pregnancy no later than GW 16 at the time of first study drug administration as determined by the principal investigator or qualified staff

Exclusion Criteria for Study Drug Administration to be Confirmed at Screening Part 2

Participants are excluded from the study if any of the following criteria apply:

1. Multiple pregnancy (> 1 fetus)
2. Known sensitivity and/or immediate hypersensitivity to any components of RLYB212 or its formulation
3. History of hypersensitivity to protein therapeutics
4. Any participant with a history of past or current intravenous immunoglobulin (IVIG) use for an underlying disease (eg, autoimmune disease)
5. Requires ongoing systemic corticosteroid or systemic immunosuppressive treatment for any reason
6. History of pre-eclampsia in a previous pregnancy
7. Participants with an in vitro fertilized pregnancy or serving as pregnancy surrogates
8. Current (or within the last 90 days) participation in another clinical study and have received an investigational drug and device within the last 90 days
9. Participants known or suspected of not being able to comply with this study protocol
10. History of any connective tissue or autoimmune or autoinflammatory disease, especially autoimmune thrombocytopenia
11. Any co-morbid medical or obstetric condition(s), laboratory abnormality, concomitant treatment, or other reason that, in the investigator's opinion, could adversely affect the safety of the participant and/or fetus, impair the assessment of study results, or preclude compliance with the study.

Non-interventional (Observational) Sub-study (IPA2202A) Eligibility and Population

It is anticipated that a limited number of participants will be enrolled in the non-interventional (observational) sub-study. Criteria for enrollment in the sub-study, with reference to the two-part Screening phase, include the following:

Table 1-1 Anticipated Eligibility Criteria for Sub-study

Screening Part 1	Screening Part 2
In the Antenatal Treatment Phase, the enrollment for the current sentinel or sequenced cohort has been fulfilled	
Results of Screening are only available after the first study drug administration window (by GW 16) has passed	
Refusal of consent to Screen Part 2	Screen Failure
---	Withdrawal of consent for Antenatal Treatment Phase

Intervention Groups and Duration

All interventional participants will receive SC RLYB212 administered using a vial and syringe.

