	SV Pt 1	SV Pt 2, if applicable ^b	EOS	
Gestational Week	<14	<16	PP10 ^c	
General Assessments				
Informed consent, eligibility confirmation, demographics, and obstetric history	X ^d	X		Gestational age in weeks is confirmed by the principal investigator or qualified staff
Other Assessments				
HPA-1a alloantibodies	X		X	
Pregnancy outcome ^d			X	Based on medical records, ie, neonatal thrombocytopenia to be sourced from the neonate's medical records

BMI = body mass index; D = day; EOS = end of study; GW = gestational week; HPA = human platelet antigen; m = minute; PI = principal investigator; PP = postpartum; SV = study visit.

^a As defined in [Table 1-2](#).

^a Screening Part 1 (presenting at GW 6 or after) women will consent to screening blood tests for HPA-1a genotyping and, if have an HPA-1b/b genotype, testing for HLA-DRB3*01:01, anti-HPA-1a alloantibody negative, and confirmation of fetal HPA-1a/b genotype via two distinct samples/analyses (as outlined in [Table 1-2](#)). At Screening Part 2 targeted after the Screening Part 1 visit, and by ~GW 16, those participants who are HPA-1b/b and HLA-DRB3*01:01 positive genotype, anti-HPA-1a alloantibody negative, and fetal HPA-1a/b genotype, will be consented to further assessments to confirm they meet all inclusion/exclusion criteria and are eligible for treatment with RLYB212 and for their pregnancy to be followed according to the requirements of the protocol.

^b In some cases, enrollment into the non-interventional (observational) sub-study will occur following SV1; therefore SV2 would not be applicable. SV2 presented for completeness.

^c Assumption is that the live birth is at 40 weeks. If this occurs earlier than 40 weeks, the assessments planned for Week 40 will be conducted at parturition.

^d For pregnancies that do not result in a live birth, the assessment of alloimmunization will be at 10 weeks from the date of the pregnancy-terminating event (ie, abortion [spontaneous/elective] or stillbirth).

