	
Cell-free fetal DNA collected for fetal genotyping is at low levels before GW 10 (<3% of total maternal circulating cfDNA and gradually increases by about 1% by Week 20). [15] Due to these low levels of fetal DNA prior to GW 16, confirmation of fetal HPA-1 genotype may come after initial dose of RLYB212 at GW 16. (Section 8.1.1 and Section 8.1.2). Consequently, some participants carrying a potentially HPA-1b/b fetus will be exposed to the loading dose of RLYB212 despite not being at risk for alloimmunization.	
The Phase 2 study (IPA2202) employs sentinel subject dosing through pregnancy followed by two sequential, sequenced cohorts. Modification of the RLYB212 dose regimen may be performed during the study based on available PK data from participant(s) with a completed pregnancy, to ensure desired steady state concentrations are maintained through pregnancy and parturition between a target lower bound of ~3 ng/mL and a target upper bound of ~10 ng/mL.For women receiving RLYB212 loading dose (0.12 mg) before the fetal genotype is definitively determined, there is a ~85% chance that the fetus will be HPA-1a/b and hence express the antigen (due to the prevalence of the HPA-1b gene and application of the Hardy-Weinberg principle in the case of unknown paternal genotype). In that case, all aspects to mitigate fetal/placental harm noted above will be in place and the loading dose will have been administered appropriately. There remains a roughly 15% chance, however, that the fetus will be determined to be HPA-1b/b, consistent with the maternal genotype. In this case, RLYB212 administration will be stopped, and the pregnancy will be followed for an additional 4 weeks for safety and PK assessment. Since RLYB212 is directed against the HPA-1a epitope, which neither mother nor fetus express, the antibody will not bind to maternal or fetal tissues. Therefore, RLYB212 is expected to pose no risk other than that of any exogenous monoclonal antibody, as outlined under “Maternal Risks” within this table.Fetal doppler ultrasound monitoring will be performed at regular intervals during the study and consistent with obstetric standard of care, to detect any evidence of placental structural abnormality, organ pathology, hemorrhage, or delayed growth in the fetus.A cord blood sample will be collected at delivery to evaluate fetal exposure to RLYB212.

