3.2 Non-Interventional (Observational)

Objective	Endpoint

To inform the frequency of HPA-1a alloimmunization among pregnant women identified at higher FNAIT risk	
Occurrence of anti-HPA-1a maternal alloimmunization at Week 10 postpartum^a

To inform the frequency of pregnancy outcomes among pregnant women identified at higher FNAIT risk	
Rate of spontaneous abortion, defined as non-deliberate fetal death which occurs prior to 19 weeks of gestationRate of elective abortion, defined as deliberate termination of pregnancy at any time in gestationRate of stillbirth, defined as non-deliberate fetal death anytime in gestation on or after 19 weeks of gestationRate of premature birth, defined as live birth prior to 37 completed weeks of gestationRate of full term birth (≥ 37 completed weeks of gestation)

To inform the frequency, where data are available, of neonatal thrombocytopenia in infants born to women who have alloimmunized, as determined by detectable anti-HPA-1a antibody at Week 10 postpartum^a	
Neonatal thrombocytopenia and severe neonatal thrombocytopenia, as determined by a platelet count $< 150 \times 10^9/L$ and $< 50 \times 10^9/L$, respectively, where data are available

^a For pregnancies that do not result in a live birth, the assessment of alloimmunization will be at 10 weeks from the date of the pregnancy-terminating event (ie, abortion [spontaneous/elective] or stillbirth).

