Screening Part 1 is an initial visit that includes the informed consent, demographic questioning (including obstetric history), and the collection of a blood sample for FNAIT testing (Table 1-2). This visit is to take place no earlier than GW 6. Individuals will consent to HPA-1 genotyping (Test 1) and, if HPA-1b/b, subsequent screening for HLA-DRB3*01:01 (Test 2), anti-HPA-1a antibodies (Test 3), and confirmation of fetal HPA-1a genotype (Test 4), as required.

Two distinct samples and analyses are performed, per industry practice, to confirm absence of the HPA-1b allele in the fetus, with timing between sampling ~2 weeks.

8.1.2 Screening Part 2

Participants who meet all eligibility criteria in Screening Part 1 (SoA, Table 1-3, ie, HPA-1b/b and HLA-DRB3*01:01 positive genotype; anti-HPA-1a alloantibody negative; fetal HPA-1a/b genotype) and who provide informed consent for Screening Part 2 (SoA, Table 1-3) will be assessed to determine if they meet all eligibility criteria to enter the antenatal treatment phase and to receive treatment with RLYB212 according to the protocol.

Dosing with RLYB212 will be initiated at Visit 3, which must occur no later than GW 16. That is, if the fetal HPA-1 genotype is pending and will not be available by the planned baseline visit at GW 16, the subject will be dosed with the initial dose of RLYB212 pending the result (of the

replicate tests), provided all other Screening Part 2 criteria are met. A second dose of RLYB212 will not be given if definitive fetal HPA-1a results are not available by Visit 4 (~GW 20). If the fetal HPA-1a genotype data become available after the initial dose of RLYB212 is given and the fetus is HPA-1b/b, ie, not at risk for HPA-1a alloimmunization, the participant will be discontinued from treatment, followed at a safety visit 4 weeks later and then discharged from the study to receive normal prenatal care and follow-up by their physician. In this case, the participant would have been determined not to be at risk for development of HPA-1a alloimmunization and FNAIT.

The study has been designed with multiple sequential cohorts ([Section 1.2.1](#)). Therefore, if a participant has been determined to be eligible for RLYB212, but the cohort has been fully enrolled, the participant will be requested to consent for the non-interventional (observational) sub-study.

Eligibility for the non-interventional (observational) sub-study is presented in [Table 1-1](#).

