9.6 Non-interventional (Observational) Sub-study

This sub-study is intended to be descriptive in nature; no hypothesis will be tested in this sub-study. Demographic and baseline characteristics will be summarized. Discrete variables will be summarized using numbers and percentages; continuous variables will be summarized using means and SD or medians and IQRs, as appropriate. Administrative tabulated summaries of study variables will be generated periodically. Data obtained from the non-interventional (observational) sub-study will be pooled with those acquired from study IPA2002 (NCT05345561) for analysis of natural history variables of the higher risk FNAIT population.

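### Sub-study spontaneous abortion is planned as a crude percentage although entry is staggered and can fall after GW 16, and platelet counts exist only where charted

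*SAP*

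**What the plan says.** Protocol Section 3.2 and SAP Section 1.1.2 give the sub-study endpoint as "Rate of spontaneous abortion, defined as non-deliberate fetal death which occurs prior to 19 weeks of gestation". Neither states a time origin, a denominator or a rule for who is at risk. The analysis text is Protocol Section 9.6: "Discrete variables will be summarized using numbers and percentages", followed by pooling with study IPA2002. SAP Section 1.1.2 says the sub-study data will be merged with IPA2002 and analyzed together, and it leaves the sub-study endpoints out of the SAP apart from disposition.

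On entry, Protocol Section 8.1.1 says of Screening Part 1: "This visit is to take place no earlier than GW 6". Fetal genotype is checked on two samples, "with timing between sampling ~2 weeks". Table 1-1 admits women when the cohort is full, when they refuse Part 2 or withdraw consent for treatment, when they fail screening, or in this case: "Results of Screening are only available after the first study drug administration window (by GW 16) has passed". No upper gestational limit is attached to that route. Table 1-4 shows screening visits before GW 14 and GW 16, but these are visit weeks, not a cap on sub-study consent. Late results are foreseen: Table 2-1 says that confirmation of fetal genotype may be delayed, "Due to these low levels of fetal DNA prior to GW 16".

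The platelet objective in Section 3.2 is "To inform the frequency, where data are available, of neonatal thrombocytopenia in infants born to women who have alloimmunized". Section 8.9.1 and Table 1-4 take these counts from medical records. The sub-study schedules no cord sample and gives no rule for infants without a count.

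**The concern.** A percentage of women with fetal death before 19 weeks is a clear risk only if everyone is followed from a common starting week. Here women start at different weeks. A pregnancy lost before identification is presumably never enrolled, since women are asked to consent after they have been identified. A woman who consents at GW 17 can contribute at most two weeks of risk but adds one full unit to the denominator. The result depends on when women happened to enter, so two datasets with the same underlying risk and different entry patterns would give different percentages.

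That matters because the stated purpose is to add natural-history frequencies for a rare condition and to pool them with another study. The platelet figure has a separate weakness. It rests on infants who happened to have a charted count, while alloimmunization is established only at Week 10 postpartum and so cannot itself prompt a count at birth.

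**Working it through.** **The plan's own follow-up figure.** Section 1.1 gives about 44 weeks per sub-study participant. Birth at 40 weeks (Table 1-4 footnote) plus 10 weeks postpartum minus first contact at GW 6 gives 40 + 10 - 6 = 44, which reproduces it. First contact at GW 16 would leave 34 weeks, and at GW 19, 31 weeks. The 44 weeks therefore describes the earliest possible screening visit.

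**Earliest entry.** GW 6 is the first screening visit, not sub-study entry. Two fetal samples about 2 weeks apart put identification at about 6 + 2 = GW 8 or later for women classified that way.

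**Spontaneous abortion, inputs.** From the documents: the window closes at GW 19, and entry can follow GW 16. Assumed, because the documents give neither: a cumulative risk of 10% over GW 6-19, and entry spread evenly over whole weeks.

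**Constant hazard.** h = -ln(1 - 0.10)/13 = 0.0081 per week. Risk from entry week e is 1 - exp(-h × (19 - e)), or zero for e ≥ 19:

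- GW 8: 8.5%
- GW 12: 5.5%
- GW 16: 2.4%
- GW 18: 0.8%
- GW 19 or later: 0

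The crude percentage is the mean of these risks over the entry weeks. For GW 8-20 (13 weeks) the risks sum to 0.519, and 0.519/13 = 4.0%.

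**Falling hazard.** The weekly hazard is multiplied by exp(-0.25), a fall of about 22% per week, and scaled to the same 10% total.

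| Even entry over | Hazard | Crude % | Risk from earliest entry week | Crude as share of that risk | Crude as share of the 10% |
|---|---|---|---|---|---|
| GW 8-20 | constant | 4.0 | 8.5 | 0.47 | 0.40 |
| GW 8-20 | falling | 1.8 | 6.0 | 0.29 | 0.18 |
| GW 12-20 | constant | 2.5 | 5.5 | 0.45 | 0.25 |
| GW 12-20 | falling | 0.7 | 2.0 | 0.34 | 0.07 |

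With an assumed risk of 5% or 15%, the last column is almost unchanged (0.39-0.40, 0.17-0.18, 0.24-0.25 and 0.07).

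**Dropping entrants at GW 19 or later.** For GW 8-20 this leaves 11 of 13 entry weeks: 4.0% × 13/11 = 4.7% (constant) and 1.77% × 13/11 = 2.1% (falling). This helps but does not remove the shortfall against 8.5% or 6.0%.

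**What delayed-entry estimation recovers.** It targets the risk from the earliest observed entry week. If that is GW 8, the target is 8.5% or 6.0%, not 10%.

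**Platelets.** Let p be the true share of affected infants, and a and u the chances that a count is charted in affected and unaffected infants. The tested-only share is p·a / (p·a + (1 - p)·u). With an assumed p = 0.30:

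- a = 0.9, u = 0.6: 0.27/0.69 = 39%
- a = 0.9, u = 0.3: 0.27/0.48 = 56%
- a = u: 30%
- a = 0.6, u = 0.9: 0.18/0.81 = 22%

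The sign depends on a against u. Bounds need no such assumption. In an invented case of 10 infants with 3 tested and 2 low, the tested-only figure is 2/3 = 67%, the lower bound 2/10 = 20% and the upper bound (2 + 7)/10 = 90%.

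**The case against.** The strongest reply is that the objective concerns women already identified at higher risk. A percentage among them describes that group, and nothing claims to estimate risk from GW 6. This stands in part: under-estimation holds only if the figure is read as an early-gestation risk. It does not cure the defect, because a percentage among identified women still mixes unequal time at risk and changes with the entry mix.

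A second reply is that the analysis belongs to the IPA2002 plan, which is not among the documents and may already handle entry week and missing counts. That stands. A reader might infer that the pooled natural-history results are biased; the documents cannot show it.

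A reader might also infer that thrombocytopenia is over-estimated because sick infants are tested more often. It is plausible, but no section says who is tested, and the protocol already discloses that counts are limited to available data. Nor do the documents support reading this as a distorted comparison with treated women. No such comparison is planned, and treated women also enter late, having to remain eligible until first dosing.

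Finally, the sub-study is expected to be small, and SAP Section 4.9 reports early termination with one participant enrolled and listings only. This limits the consequence. Section 4.9 does not say whether the sub-study pooling is cancelled or how many women the sub-study holds.

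**Conclusion.** The point holds in a limited form. The planned crude percentage for spontaneous abortion mixes unequal time at risk and falls below the risk from early gestation. That direction held under both hazard shapes tried and follows from staggered entry. Its size is not determinable: the shares of 0.07 to 0.40 of the GW 6-19 risk come from assumed event rates and entry patterns, and do not measure this study's bias. It also assumes that pregnancies lost before identification do not enter the sub-study.

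For neonatal thrombocytopenia, the supportable conclusion is that the tested-only percentage may be selective, with unknown direction. An effect on the pooled data remains unverified without the IPA2002 plan. This is a change that should be made if the pooling goes ahead, not a threat to the interventional study.

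**What to change.** In Protocol Section 9.6, or by reference to the IPA2002 plan if it already does this:

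- Derive gestational week at sub-study consent from the gestational age confirmed at screening (Table 1-4) and the consent date, and carry it into the pooled dataset.
- Restrict the spontaneous-abortion denominator to women entering before GW 19.
- Report outcomes by entry week. If numbers allow in the pooled data, report cumulative incidence by gestational age with delayed entry at consent, treating the other pregnancy outcomes (such as elective abortion) as competing events. State that risk is estimated only from the earliest observed entry week.
- For infants of alloimmunized women, report how many have and lack a platelet count. Beside the tested-only percentage, give a lower bound (low counts over all such infants) and an upper bound (low counts plus untested, over all such infants).

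The cost is small. Outcome dates are already collected (Sections 8.9.1 and 8.9.2), so this is one derived variable and analysis wording. The estimates are less simple to read, and delayed-entry estimates will be unstable where few women are at risk in the early weeks. With very small numbers, a table by entry week is enough.
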